4.3 Eligibility

All eligibility data will be listed in full.

4.4 Protocol Deviations

Prior to database lock, Targovax ASA will review the individual deviations and classify them as major or minor during a data review meeting. Details of all protocol deviations including start and end dates, deviation category (treatment deviation, subject not withdrawn as per protocol requirements, eligibility criteria not met, assessment outside time window), classification as major/minor and deviation details will be listed separately for patients in Part I and Part II.

4.5 Background and Demographic Characteristics

For sections 4.5.1 to 4.5.5, including disposition, the data will be summarized for each treatment group (Part I and Part II) and Overall.

4.5.1 Demography

Demographic characteristics (age, sex and race) and body measurements (height and weight) will be summarised.

Age will be calculated in years from date of birth to the date of informed consent.

Individual patient demographic and baseline data, including pregnancy test results and details, will be listed.

4.5.2 Medical History of Colorectal Cancer

Details of colorectal cancer history will include:

- Diagnosis at time of screening
- Time from diagnosis primary advanced disease or recurrent disease, whichever is latest, to first investigational medicinal product (IMP) administration (weeks), calculated as (date of first IMP administration – date of diagnosis primary advanced disease or recurrent disease, whichever is latest + 1)/7
- Time from diagnosis primary advanced disease or recurrent disease, whichever is latest, to surgery (weeks), calculated as (date of surgery – date of diagnosis primary advanced disease or recurrent disease, whichever is latest, + 1)/7

- Tumour, nodes, metastasis (TNM) stage at diagnosis primary advanced disease and at diagnosis of recurrent disease
- Number and percentage of patients with Kirsten rat sarcoma (KRAS) mutation detected (yes/no)
- Mutation type (12/13) and specific KRAS mutation, where percentages are based on the number of patients with oncogenic KRAS confirmation
- Extent of disease

All colorectal cancer medical history details will be listed.

4.5.3 Medical History (Excluding Colorectal Cancer)

Medical history events will be coded using the latest Medical Dictionary for Regulatory Activities (MedDRA) version.

Previous medical history is defined as anything that started and ended prior to the first IMP administration. Medical history that is ongoing at the first IMP administration or started after first IMP administration will be deemed to be current. If medical history dates are incomplete and it is not clear whether the medical history was ongoing, it will be assumed to be current.

The number and percentage of patients who had any previous or current medical history will be presented by system organ class (SOC) and preferred term (PT) SOCs will be ordered in decreasing frequency of the total number of patients with the medical histories reported in each SOC and PTs will be ordered within a SOC in decreasing frequency of the total number of patients with each medical history.

All medical history events (excluding colorectal cancer) will be listed by SOC and PT.

4.5.4 Previous Cancer Treatment

Previous cancer treatment will be divided into treatment before and after recurrence of the disease.

The number and percentage of patients with any previous cancer treatment and with each type of cancer therapy will be presented separately for previous cancer treatment administered before and after recurrence of disease but before entering the study.

All previous cancer treatment data will be listed in full and previous cancer treatment after recurrence of disease will be flagged.

4.5.5 Prior and Concomitant Medications

Prior and concomitant medications will be coded according to the latest World Health Organization Drug dictionary (WHO Drug) version.

Prior medications are defined as those that started and ended prior to the first IMP administration. Medications that are ongoing at the first IMP administration or started after first IMP administration will be deemed to be concomitant medications. If medication dates are incomplete and it is not clear whether the medication was concomitant, it will be assumed to be concomitant.

The number and percentage of patients who had any concomitant medications will be presented separately by medication class and standardised medication name sorted alphabetically.

All prior and concomitant medication data will be listed. All medications which start up to four weeks prior to the first dose of IMP will also be flagged in the listings.

4.5.6 Diagnostic Imaging

Details of diagnostic imaging collected at screening will be listed.

4.6 Administration of Investigational Product

All details of GM-CSF, TG02 and pembrolizumab administration are described in Section 5.1

4.7 Surgery

All surgery data will be listed in full.

5 SAFETY EVALUATION

All safety evaluations will be performed on the safety analysis set unless specified otherwise.

The safety endpoints of interest are the incidence and severity of AEs by NCI Criteria for Adverse Events (CTCAE v4.03) and changes from baseline in laboratory variables, physical examination, vital signs and European Cooperative Oncology Group (ECOG) performance status.

5.1 Study Drug Exposure

The duration of exposure to TG02-treatment in days, as well as the total dose of GM-CSF and the total dose of TG02 separately for vaccination, DTH testing and vaccination and DTH testing combined will be summarised.

Duration of exposure to study drug will be calculated as: date of administration of the last dose – date of administration of the first dose of study drug + 1.

The dose of study drug administered for DTH testing, vaccination and DTH testing and vaccination combined will be calculated in the following way:

- the total dose of GM-CSF will be calculated as the sum of the dose administered at each visit
- the total dose of TG02 for DTH testing will be calculated as the sum of the dose administered for DTH testing at each visit
- the total dose of TG02 for vaccination will be calculated as the sum of the dose administered for vaccination at each visit
- the total dose of TG02 for vaccination and DTH testing combined will be calculated as the sum of the dose administered for vaccination at each visit + sum of dose administered for DTH testing at each visit,

where the dose administered is calculated as dose strength*volume.

The number of injections of GM-CSF and TG02, the number of injections of TG02 for DTH testing and the total number of injections (GM-CSF and TG02, including DTH testing) will be summarised. The number and percentage of patients with dose delays and discontinuation with GM-CSF/TG02, together with the frequency and reasons for such dose modifications will be summarised by visit and overall. A summary of whether TG02-treatment was received (yes/no) will also be presented by visit.

For all patients in Part II of the study, the duration of exposure to pembrolizumab, the number of injections of pembrolizumab, as well as the total dose and reason for reduction, delay or discontinuation with pembrolizumab will be summarised. The total dose of pembrolizumab administered is the sum of the doses administered at each injection.

All IMP administration data will be listed.

5.2 Adverse Events

Any events that are unequivocally due to progression of disease will not be reported as AEs or SAEs.

Adverse events will be coded according to the latest MedDRA dictionary version.

A treatment-emergent adverse event (TEAE) is defined as an AE with start date/time on or after the first administration of IMP. A pre-treatment AE is defined as an AE with start date/time prior to the first administration of IMP.

There will be no imputation of unknown dates for the calculation of duration or study day. However, for sorting and assignment, if the start date is unknown then it will be assumed to be treatment emergent unless the partial start date or other data (i.e. stop date) indicates differently.

Assessment of AE severity will be based on the NCI CTCAE which includes five grades, with grade 5 being death. If the severity of an event changes during the course of that event, only the maximum severity/grade will be summarised in the tables.

The relationship to each IMP (TG02, GM-CSF, pembrolizumab) is assessed as not related or related.

An overview summary table will summarise the number of events and the number and percentage of patients with at least one of the following TEAEs:

- total TEAEs
- total serious TEAEs
- total IMP related serious TEAEs
- TEAEs leading to TG02 and GM-CSF withdrawal
- TEAEs leading to pembrolizumab withdrawal
- TEAEs leading to study withdrawal
- TEAEs leading to death
- TEAEs by severity

- TEAEs by relationship to each IMP (related, not related) separately
- SAEs by relationship to each IMP separately

The number of events and the number and percentage of patients experiencing TEAEs will be presented by SOC and PT for the following TEAEs:

- Total TEAEs: If a patient experienced more than one TEAE, the patient will be counted once for each SOC and once for each PT. This summary will be repeated for serious TEAEs only.
- Total TEAEs by severity: If a patient experienced more than one TEAE, the patient will be counted once for each severity experienced during the study.
- TEAEs by relationship to each IMP: If a patient experienced more than one TEAE, the patient will be counted once for each SOC and once for each PT at the closest relationship to study drug. This summary will be repeated for serious TEAEs only.
- TEAEs related to TG02 by severity. For this table, grade 1 and 2 events will be pooled. If a patient experienced more than one TEAE, the patient will be counted once for each severity experienced during the study. TEAEs related to GM-CSF, TEAEs related to TG02 and/or GM-CSF, TEAEs related to TG02 and/or GM-CSF only (i.e. events not related to pembrolizumab) and TEAEs related to pembrolizumab only will be summarised in an identical fashion.
- TEAEs leading to death.

In all of the tables described above, SOC and PT will be presented in decreasing frequency of the total number of patients with TEAEs.

All TEAEs will be listed with a separate listing for pre-treatment AEs. Separate listings of serious TEAEs and pre-treatment SAEs will also be presented.

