Patients will be evaluated for safety at scheduled visits until surgery and at the end of study visit approximately 4 weeks after surgery. In addition, after any TG02-treatment the patients will be monitored for heart rate and blood pressure at 5, 10 and 30 minutes and then every 30 minutes thereafter for up to 2 hours post administration.

A FDG PET-CT will be performed before TG02-treatment is initiated (baseline scan should be within the last 4 weeks prior to first TG02-treatment) and a second scan as close as possible before surgery.

Tumour samples for assessment of immune response will be taken pre TG02-treatment in the form of a study specific biopsy and at time of surgery by analysis of the resected tumour tissue. If a pre TG02-treatment biopsy has been taken for diagnostic workup at the hospital, this biopsy, if adequate for the study specific immune analysis and no intervening treatment has been given, can be used as the study specific biopsy if taken within the last 4 week prior to first TG02-treatment. If for any reason the patient does not proceed to surgery, a biopsy will be obtained at the time of planned surgery if possible. In addition, archival biopsy samples from both initial staging (primary diagnosis) and re staging will be utilised, as needed. In the patient information sheet and informed consent form (PIS/ICF), patients will be asked to give consent to the use of archived biopsy material. These archival samples will be used to assess RAS-mutation status and other baseline immune assessments.

Delayed-Type Hypersensitivity (DTH) tests will be performed at week 1, week 4, week 6 and week 8 (if surgery is scheduled for week 8, the DTH test should be performed two days before surgery). If surgery is scheduled for after week 10, and the patient has had only negative DTH tests up to and including week 8, an additional DTH test should be performed at week 10.

Blood samples will be collected for in vitro assessment of TG02-specific immune responses (Immunology sample, PBMC) will be collected at baseline (Day 1, Week 1) and week 8 (Day 64). If surgery is scheduled to occur after week 10, a third sample will be taken as close as possible to the date of surgery.

In total, the study will enrol up to 16 patients for Part I and II.

Subject population: The target population is patients with locally advanced primary and recurrent oncogenic KRAS exon 2 mutant colorectal cancer eligible for radical pelvic surgery at time of enrolment.

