6.4.3. End of Study visit (Up to 6 weeks after surgery)

End of study visits to be scheduled during the hospitalized post-operative recovering period, up to 6 weeks after surgery.

- Physical exam (review of the major body systems, vital signs (weight, heart rate, blood pressure and tympanic body temperature)
- ECOG Performance status
- Blood samples for routine haematology and serum biochemistry ([Table 9-1](#)) or will be recorded if already available in the patient medical record.
- Adverse events and concomitant medications deemed to be related to TG02-treatment

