Hospitalisation for administrative reason (for observation or social reasons) is allowed at the investigator's discretion and will not qualify as serious unless there is an associated adverse event warranting hospitalisation (see [Appendix I](#) and [Appendix II](#) for additional safety information).

The causality of AE/SAEs (i.e., their relationship to trial treatment) will be assessed by the individual investigators at each trial centre who must while completing the CRF answer yes/ no to the question 'do you consider that there is a reasonable possibility that the AE/SAE may have been caused by the investigational drug?'

Any events that are unequivocally due to disease recurrence must not be reported as AEs.

The specialist group handling the pharmacovigilance for the study is:

[REDACTED]

The [REDACTED] is specialised and has the appropriate expertise in handling and reporting SAEs.

9.2.1.2. *Adverse Event Reporting*

For the purpose of this trial, any detrimental change in a patient's condition, subsequent to their entry into the trial and during the 28-day follow-up period after the final treatment, should be considered an AE.

The development of a new cancer should be regarded as an AE. New cancers are those that are not the primary reason for the administration of the trial treatment and have been identified after the patient's inclusion into this clinical trial.

Any events that are unequivocally due to disease recurrence must not be reported as AEs.

If the same AE occurs at several investigation times in one patient, then the AE in question must be documented and assessed as new each time.

All AEs are to be recorded on the CRFs provided and Serious Adverse Events also on the Serious Adverse Event Form. A description of the event, including its severity, duration, any action taken (e.g. treatment and follow-up tests) and the outcome is to be provided, along with the investigator's assessment of the relationship to the trial treatment. AEs and laboratory values will be graded according to the NCI Criteria for Adverse Events (CTCAE) (v4.03: June 14, 2010) and recorded on the appropriate CRF page.

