Additional information will be requested, if necessary, by the Trial Physician within 5 days of the receipt of the SAE report. This is to ensure that the initial reporting of SAEs is made to the regulatory authorities within the required time-frame. All withdrawals from trial treatment must be notified to the trial physician. Withdrawals from treatment due to a new, previously unreported SAE must be notified to the Trial Physician, along with the SAE. Withdrawal from trial treatment for a previously reported SAE can be made within the 7 days after the decision has been made to withdraw the patient and for a non-serious AE within 21 days of the decision to withdraw. After withdrawal from treatment patients must be followed up for AEs for 28 days after the last dose of trial medication. All SAEs recorded during that period must be reported to the safety group, and followed up until resolved unless in the Investigator's opinion the condition is unlikely to resolve due to the patient's underlying progressive disease.

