11.6.1. Primary Endpoints

11.6.1.1. Safety Endpoints

Adverse events

All adverse events will be classified by MedDRA, version 19 or higher.

A treatment-emergent adverse event (TEAE) is defined as an AE with start date/time on or after the first administration of investigational medicinal product (IMP). A pre-treatment AE is defined as an AE with start date/time prior to the first administration of IMP.

The following summary tables will be created, reporting number of events and number of patients with events by MedDRA System Organ Class and Preferred Term for the TEAEs:

- total TEAEs
- total serious TEAEs
- total IMP related serious TEAEs
- TEAEs leading to GM-CSF/TG02 withdrawal
- TEAEs leading to study withdrawal
- TEAEs leading to death
- TEAEs by severity
- Related TEAEs by severity
- TEAEs by relationship to each IMP (related, not related) separately

Safety laboratory data

Numerical laboratory data, separately for each parameter, will be summarized in terms of descriptive statistics, as described in [section 11.4](#), by time point of measurement, for absolute value, absolute and relative change from baseline. Further, number of patients with abnormal and/or clinical significant values will be presented by time point.

Vital signs

Blood pressure, heart rate and body temperature will be summarized in terms of descriptive statistics, as described in [section 11.4](#), by time point of measurement, for absolute value, absolute and relative change from baseline.

ECG

Number of patients with abnormal findings in ECG evaluation will be reported by time point of measurement.

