5.6 Physical Examination and ECOG Performance Status

The number and percentage of patients will be presented by ECOG performance status and study visit. In addition, a shift table presenting the shift from baseline in ECOG performance status by visit will be produced. The baseline value will be defined as the last scheduled or unscheduled value collected prior to first dose of IMP. Assessments carried out on the day of first IMP administration are considered to have taken place before the IMP administration, if the corresponding times have not been recorded. For post baseline, only data from scheduled visits will be included in the tables. Patients who attended a visit but have no ECOG data available will be included in the missing and total categories. Patients who withdrew prior to the visit will not be included in the summary for that visit and will be excluded from the denominator for calculation of percentages at that visit.

A listing will present ECOG assessment date and ECOG performance status together with whether a physical examination was performed and the date and time of examination.

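### The TEAE tables run through radical pelvic surgery with no end date and no split at surgery, while two conflicting rules decide which post-operative events are collected

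*SAP*

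**What the plan says.** SAP 5.2 defines the event class by its start alone: "A treatment-emergent adverse event (TEAE) is defined as an AE with start date/time on or after the first administration of IMP". Protocol 11.6.1.1 has the same definition. Neither sets an end. SAP 4.7 only lists the surgery data, and no table in SAP 5.2 to 5.6 uses the surgery date. SAP 4 shows the two Parts side by side.

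Collection is governed by several rules:

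- Protocol 9.2.1.2, all causes: a detrimental change after entry and "during the 28-day follow-up period after the final treatment, should be considered an AE".
- The same section, for patients withdrawn from treatment: "patients must be followed up for AEs for 28 days after the last dose of trial medication".
- The same section requires every SAE to be reported, related or not.
- Appendix I exempts planned operations and admissions for pre-existing disease. It does not exempt their complications.
- Protocol 6.4.3, for the only post-operative visit: "Adverse events and concomitant medications deemed to be related to TG02-treatment". Table 6-1, footnote a, repeats this, and Protocol 9.2.2 limits laboratory changes reported at follow-up to those judged related.

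That visit is described as follows: "End of study visits to be scheduled during the hospitalized post-operative recovering period, up to 6 weeks after surgery". The synopsis instead places safety evaluation "at the end of study visit approximately 4 weeks after surgery". ECOG, laboratory values and vital signs are taken at it and summarised by visit. For ECOG, "a shift table presenting the shift from baseline in ECOG performance status by visit will be produced".

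**The concern.** Safety is the first primary objective, and every patient is expected to have a major operation shortly after the last dose. Protocol 4.5 itself describes resection of pelvic recurrence as carrying significant operative risk. If events after surgery are counted with events during treatment, the all-causality tables mix drug effects with surgical morbidity. The mixture would also vary with the gap between last dose and operation, which is set by surgical scheduling and not by the drug. With 4 to 6 patients in Part I and up to 10 in Part II, one complication visibly changes a percentage.

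**Working it through.** The plan gives no figure to reproduce: there is no formal sample size calculation and the analysis is descriptive. The check is the number of post-operative days inside the 28-day window, followed by a comparison of the collection rules.

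**Inputs (nominal days, visit windows ignored)**

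- AE follow-up: 28 days after final treatment or last dose (Protocol 9.2.1.2).
- Surgery: Day 50 to Day 92 (Protocol 6.4.2, Table 6-1).
- TG02-treatment: Days 1, 8, 15, 22 and 36, and Day 64 if surgery is after Week 10 (Protocol 6.4.2).
- Pembrolizumab, Part II only: Days 22 and 36, Day 50 if surgery is after Day 50, and Day 64 if surgery is after Day 64 (Protocol 6.4.2; Table 6-1, footnotes s and t).
- Week 8 DTH injection of TG02, both Parts: Day 50, or about 48 hours before a Week 8 operation, taken as Day 48 (Table 6-1, footnote b).

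**Formula:** post-operative days = (day of last dose + 28) − day of surgery.

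| Surgery | Part I, DTH not counted | Part II, DTH not counted | Both Parts, DTH counted |
|---|---|---|---|
| Day 50 | 36+28−50 = 14 | 36+28−50 = 14 | 48+28−50 = 26 |
| Day 51 | 36+28−51 = 13 | 50+28−51 = 27 | 50+28−51 = 27 |
| Day 57 | 36+28−57 = 7 | 50+28−57 = 21 | 50+28−57 = 21 |
| Day 63 | 36+28−63 = 1 | 50+28−63 = 15 | 50+28−63 = 15 |
| Day 64 | 36+28−64 = 0 | 50+28−64 = 14 | 50+28−64 = 14 |
| Day 65 | 64+28−65 = 27 | 64+28−65 = 27 | 64+28−65 = 27 |
| Day 92 | 64+28−92 = 0 | 64+28−92 = 0 | 64+28−92 = 0 |

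**Between patients.** The window holds 0 to 27 post-operative days on either reading. The conditional Week 10 DTH injection is not modelled. If it counted and were given 48 hours before surgery (Table 6-1, footnote i), that patient would have 28−2 = 26 days, within the same range.

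**Between Parts.** With DTH not counted, the difference for any surgery day s from 51 to 64 is (50+28−s) − (36+28−s) = 14 days. It is zero on all other surgery days, and zero throughout if the Week 8 DTH injection counts.

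**Does the DTH injection count?** Protocol 4.2 defines TG02-treatment as the GM-CSF/TG02 combination, which leaves DTH injections out. Protocol 9.2.1.2 speaks of final treatment in one place and of the last dose of trial medication in another. Protocol 8.2 calls the DTH injection a dose, and SAP 5.1 includes it in the combined TG02 dose and the total injection count. The documents do not settle the question.

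**Weight of one patient.** One patient with a complication moves a percentage by 1/4 = 25 points, 1/6 = 16.7 points or 1/10 = 10 points.

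**Collection rules compared.** Take an unrelated, non-serious wound complication 10 days after surgery and inside the 28 days. Under Protocol 9.2.1.2 it is an AE, and under SAP 5.2 therefore a TEAE. If the site records only what 6.4.3 and Table 6-1 ask for at the post-operative visit, it is not collected. The same complication, if serious, is reported under either rule. The SAP does not say which rule prevails.

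**The case against.** The best defence is that the plan already offers ways to separate the sources. SAP 5.2 tabulates TEAEs by relationship to each IMP and gives severity tables for related events. All TEAEs and all surgery data are listed, so with at most 16 patients a reader can place each dated event relative to surgery. No formal comparison of the Parts is planned. This confines the problem to the all-causality tables, and it would be wrong to say that the safety data cannot be interpreted. It is not a full answer: relatedness is an open-label investigator judgement, and Appendix II directs that ambiguous cases be treated as having a reasonable possibility of causation. Post-operative fever or infection could therefore default to related.

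Three stronger readings are tempting, and the documents do not support them.

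- A reader might infer that all surgical morbidity becomes treatment-emergent. The related-only rule at the post-operative visit means that unrelated, non-serious events may never be collected there. What the documents show is a conflict between rules.
- A reader might infer that Part II necessarily has the longer post-operative window. That holds only for surgery on Days 51 to 64, and only if the Week 8 DTH injection is not final treatment.
- A reader might infer that ECOG, laboratory and vital-sign summaries are contaminated throughout. They are tabulated by visit, and the end-of-study visit follows surgery, so post-operative values sit in their own row. The fault there is a missing label.

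**Conclusion.** The point stands for the all-causality TEAE tables. The definition has no end, nothing is split at surgery, and post-operative complications within 28 days of the last treatment, together with all reported SAEs, can enter the total, serious, severity and death counts. The exposure is 0 to 27 post-operative days between patients. The 14-day difference between Parts is conditional, as shown. The related-only rule conflicts with the 28-day all-cause rule, so the handling of unrelated, non-serious surgical events depends on site practice.

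These figures rest on nominal visit days and on dosing as scheduled. They show how much post-operative time is exposed, not how many complications will occur, since the documents give no complication rate. The ECOG, laboratory and vital-sign issue is limited to labelling. The end-of-study timing (about 4 weeks in the synopsis and 6.4.4; approximately 6 and also within 6 weeks in 6.4; in hospital and up to 6 weeks in 6.4.3) is a lesser wording matter, since 4 weeks lies within an upper limit of 6.

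**What to change.** 1. SAP 5.2: derive a flag from the surgery date and present the TEAE tables within each Part by onset before surgery and onset on or after surgery. Show both, so that late drug effects stay visible. Neither period should be the sole basis for describing safety: the pre-surgery period also varies in length, because surgery ranges from Day 50 to Day 92, and it would leave out delayed effects.
2. SAP 5.2: define the end of the TEAE window, and define final treatment, stating whether DTH injections count.
3. Protocol: reconcile the all-cause 28-day rule in 9.2.1.2 with the related-only rules in 6.4.3, Table 6-1 footnote a and 9.2.2, and have the SAP state which rule its tables follow.
4. SAP 5.3, 5.4 and 5.6: label the end-of-study row as post-surgery and give days since surgery.
5. Protocol: state one timing for the end-of-study visit across the synopsis, 6.4, 6.4.3 and 6.4.4.

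The cost is wording, one derived variable from a date already collected, and longer AE tables.

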9.2.1.1. Definitions

An adverse event (AE) is the development of an undesirable medical condition or the deterioration of a pre-existing medical condition in a patient under clinical investigation who has been administered an investigational pharmaceutical product (in this case GM-CSF/TG02 but which does not necessarily have a causal relationship with this treatment. An undesirable medical condition can be symptoms (e.g., nausea, chest pain) signs (e.g., tachycardia, enlarged liver) or abnormal results of an investigation (e.g., laboratory findings, ECG). An AE can include any undesirable condition occurring at any time after inclusion in the study, even if no trial treatment has been administered or recently administered. A grading severity scale is provided for each AE term. NCI Criteria for Adverse Events (CTCAE) (v4.03: June 14, 2010) includes five grades (1-5), with grade 5 being death.

Any events that are unequivocally due to disease recurrence must not be reported as AEs.

A serious AE (SAE) is an event that is known with certainty, or suspected with good reason, to constitute a threat to life or to cause severe or permanent damage. A SAE can occur during any phase of the trial and at any dose of the investigational product. This is particularly true for an AE that:

- results in death
- is immediately life-threatening
- requires patient hospitalisation or prolongation of existing hospitalization
- results in persistent or significant disability/incapacity or
- is a congenital anomaly/birth defect
- is an important medical event that may have jeopardised the patient or may have required medical intervention to prevent one of the outcomes listed above.

Medical and scientific judgment is to be exercised in deciding on the seriousness of a case. Important medical events may not be immediately life-threatening or result in death or hospitalisation, but may jeopardise the patient or may require intervention to prevent one of the listed outcomes in the definitions above. In such situations, or in doubtful cases, the case should be considered as serious. Drug misuse and drug overdose and should be regarded as serious, even if they may not result in the above mentioned outcomes.

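### The TEAE definition has no worsening clause, so an AE that starts between consent and first dose and rises in grade on treatment is missing from the TEAE summary tables if kept as one record

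*SAP*

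**What the plan says.** SAP 5.2 gives the rule and its converse: "A treatment-emergent adverse event (TEAE) is defined as an AE with start date/time on or after the first administration of IMP" and "A pre-treatment AE is defined as an AE with start date/time prior to the first administration of IMP". Protocol 11.6.1.1 uses the same rule: "A treatment-emergent adverse event (TEAE) is defined as an AE with start date/time on or after the first administration". The SAP's only refinement is that an event with an unknown start date defaults to treatment-emergent unless other data point the other way. Neither document mentions worsening after the first dose.

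On changing severity, SAP 5.2 says: "If the severity of an event changes during the course of that event, only the maximum severity/grade will be summarised in the tables". Its tables are confined to TEAEs: "An overview summary table will summarise the number of events and the number and percentage of patients with at least one of the following TEAEs". The tables by system organ class (SOC) and preferred term (PT) have the same limit. Pre-treatment AEs and pre-treatment SAEs each get a listing.

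Two protocol rules bear on how the record is made. Section 9.2.1.1 includes in the AE definition "the deterioration of a pre-existing medical condition in a patient under clinical investigation". Section 9.2.1.2 says of an AE found at several investigation times: "then the AE in question must be documented and assessed as new each time".

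**The concern.** Adverse events are a primary endpoint (protocol 6.1). Worsening on treatment of something already present at Day 1 is part of what the safety objective should show. Under the rules above, an AE that opens in screening and is carried on one line is classified once, by its start. Whatever grade it reaches later, it stays pre-treatment.

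Pre-dose AEs are foreseeable. Patients are on study from consent (protocol 6.2), screening runs over 14 days (6.4) and normally includes a core biopsy (6.4.1), and the SAP plans listings for pre-treatment events.

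For symptoms and clinical findings, the AE tables are the main summary. SAP 5.6 lists only whether and when a physical examination was done, not what it found. The protocol synopsis promises summaries of serious events and of deaths in the study period without limiting them to treatment-emergent events. The SAP tables could miss a pre-dose event that becomes serious or fatal after dosing.

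**Working it through.** The plan states no AE rate or calculation on this point, so there is no figure to reproduce. The check applies each rule to one assumed history, then sizes the effect.

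**Inputs.**
- Assumed AE: onset Day -3 at grade 1, grade 3 from Day 15, ongoing.
- Treatment-period assessments (protocol 6.4.2): Days 1, 8, 15, 22, 36 and 50, plus Day 64 if surgery is after week 10.
- Timing on Day 1 (protocol Table 6-1, footnote h): the marked assessments come before treatment.
- Group sizes (SAP 3.4): 4-6 in Part I, up to 10 in Part II.

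**1. One record, SAP 5.2 as written.** Start Day -3 is before first dose, so there are 0 TEAEs. The event is in the pre-treatment listing and in no TEAE table.

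**2. One record, with a worsening clause.** The grade rises on Day 15, after first dose: 1 TEAE, tabulated at grade 3.

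**3. Worsening entered as a new AE, relying on protocol 9.2.1.1.** Start Day 15: 1 TEAE. Neither document tells sites to open a new line, and the SAP's maximum-grade rule presumes that they do not.

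**4. Re-entered at each assessment, one reading of protocol 9.2.1.2.** The Day 1 entry is made before dosing and is pre-treatment. The treatment-emergent records are Days 8, 15, 22, 36 and 50 = 5, plus Day 64 = 6.

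The same history therefore gives 0, 1 or up to 6 TEAE records, depending on a recording convention that is not stated.

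**5. Patients versus events.** SAP 5.2 counts a patient once per SOC and once per PT, so the 5 or 6 records in step 4 still make one patient. They inflate event counts. In the severity tables the patient counts once for each grade experienced.

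**6. Size of an omission.** Change in incidence = 100 × 1/n:
- n = 4: 100/4 = 25.0 points
- n = 6: 100/6 = 16.7 points
- n = 10: 100/10 = 10.0 points

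This applies to a row in which the patient has no other qualifying event. A row for any TEAE may not move at all.

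**The case against.** The strongest reply is that the documents already offer a route. Deterioration is itself an AE under protocol 9.2.1.1, worsening on physical examination is an AE under 9.2.3, and laboratory values of grade 3 or higher must be reported as AEs in the treatment period (9.2.2). If a site dates the new AE at the worsening, it is a TEAE. That stands as a possibility. It depends on eCRF instructions that protocol 10.1 says will be provided, and it conflicts with the SAP's one-event rule.

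Several stronger conclusions that a reader might draw are not supported:

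- *The event leaves every safety table.* It does not. Laboratory CTC-grade shifts, vital-sign changes and ECOG shifts are tabulated from baseline (SAP 5.3, 5.4, 5.6), reasons for dose delay or discontinuation are summarised (SAP 5.1), and the event stays in the listings.
- *Lingering chemo-radiation toxicity is generally lost.* Patients consent after such treatment (protocol 4.5, 6.2). Toxicity open at consent would usually be medical history (SAP 4.5.3), and its deterioration would be a new AE. The gap is confined to AEs that arise between consent and first dose. Their number is uncertain: in the available copy of Table 6-1, the AE row has no screening mark.
- *Events are both dropped and multiplied.* These are alternatives. A record re-entered after dosing is not lost, and one not re-entered is not multiplied. The wording in 9.2.1.2 can also fairly be read as covering recurrences only.
- *The safety review is compromised.* The Safety Steering Committee reviews all AEs and SAEs (protocol 6.2), not only TEAEs.

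It is also true that the study is descriptive, so no test or threshold changes, and that listings for 4 to 10 patients can be read in full.

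**Conclusion.** The concern holds in a limited form and should be fixed. Both documents set treatment-emergence by start date and time with no worsening clause, and the SAP holds a changing event as one event. An AE arising between consent and first dose, kept as one record and increasing in grade after dosing is therefore missing from the TEAE summaries of a primary endpoint. For each affected patient, the relevant incidence is understated by 25 points (n=4), 16.7 points (n=6) or 10 points (n=10), provided that no other event of that patient fills the row.

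The recording rules add a second ambiguity: up to 6 treatment-emergent event records for the same history if 9.2.1.2 covers persisting events, with the patient still counted once per SOC and PT. The harm is to the reported results. How many patients would be affected cannot be told from the documents.

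**What to change.** - **SAP 5.2 and protocol 11.6.1.1:** define a TEAE as an AE that starts on or after first IMP, or that started earlier and increases in CTCAE grade on or after first IMP. Tabulate it at its maximum on-treatment grade.
- **Protocol 9.2.1.2:** state that a persisting AE is one record and that only a recurrence after resolution is a new AE. Choose one way to capture worsening, either a date for each grade increase or a new line opened at worsening, and use it in both parts.

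The cost is a few sentences and, if the first option is chosen, one eCRF date. TEAE counts will rise slightly. Protocol 4.2 reports four patients already treated, so grade-increase dates may have to be retrieved for them. SAP section 1 already provides for a review before database lock, which is a natural point to make the SAP change.
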